$$\text{eGFR} = 175 \times \text{Serum Creatinine}^{-1.154} \times \text{Age}^{-0.203} \times [1.212 \text{ if Black}] \times [0.742 \text{ if Female}]$$

Additional details about the eGFR equations and the standardized creatinine assays will be provided in the SOM.

Each subject will attend Screening visit(s) when the inclusion/exclusion criteria will be assessed. Eligible subjects will be admitted to the study site at Baseline (Day -2), where eligibility for enrollment into the study will be confirmed as needed. All baseline safety evaluation results must be available and reviewed prior to dosing when screening is performed more than 7 days prior to dosing. Each subject will receive once daily LIK066 at 50 mg dose for 7 days. Meal contents including carbohydrates and salt will be standardized from Day -2 to the morning of Day 2, and then from Day 5 to Day 8, [REDACTED]

[REDACTED] Detailed information on meal recommendation is provided in the SOM. Baseline twenty-four hour urine samples will be collected. Study participants must be fasted for approximately 10 hours before Day 1 dosing of LIK066. Standardized breakfast will be provided immediately after the administration of LIK066 in the morning.

Following the first dose on Day 1, subjects will remain domiciled for at least 24 hours for collection of urine and blood samples for urinary glucose excretion, pharmacokinetic, pharmacodynamic and safety assessments. Subjects will either remain domiciled (mandatory for subjects with severe renal impairment) or return in the morning to the study site every day (Day 3 to Day 5) to receive their medication after approximately 10-hour fasting overnight, per the investigator discretion as described in the SOM. A standardized breakfast will be served immediately after administration of LIK066 every day. Subjects will be domiciled from Day 5 and will be fasted for approximately 10 hours before the final dose on the morning of Day 7 at the site. Subjects will remain domiciled up to Day 8 to complete 24-hour collection of urine and blood for urinary glucose excretion, pharmacokinetic, pharmacodynamic and safety assessments after the final dose. Blood and urine samples for pharmacokinetic assessments will be taken on Days 9, 10 and 11 (up to 96 hours post the final dose). Study completion evaluations will be performed after the last pharmacokinetic assessment is completed (Day 11), or in the case of early termination, prior to discharge from the study site.

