18. History of significant gastrointestinal surgery that could affect intestinal glucose absorption (e.g. bariatric surgeries including, Roux en Y gastric bypass, sleeve gastrectomy, Nissen fundoplication).
19. Subjects who experienced ketoacidosis, lactic acidosis, or hyperosmolar coma within 6 months of Screening Visit, or between Screening Visit and Baseline Day -1.

20. Use of prohibited medications:

- Use of SGLT2 or alpha-glucosidase inhibitors within 2 weeks prior to dosing and during the study. If treated with other oral antidiabetic medications, patients must be on a stable regimen for at least 6 weeks prior to starting the study treatment
- Use of potassium-binders within 3 days prior to dosing and during the study
- Treatment with drugs that have a high incidence of diarrhea during the study
- Chronic systemic steroid treatment or systemic steroids for > 7 consecutive days for worsening of an underlying condition within 4 weeks of screening. Use of topical or inhaled steroids is permitted
- Strong inhibitors of CYP3A4/5 including boceprevir, clarithromycin, conivaptan, grapefruit juice, indinavir, itraconazole, ketoconazole, lopinavir, nefazodone, nelfinavir, posaconazole, ritonavir, saquinavir, telaprevir, telithromycin, and voriconazole within 7 days prior to the study treatment and during the study
- Strong CYP3A inducers including avasimibe, carbamazepine, phenytoin, rifampin, St. John's wort within 7 days prior to the study treatment and during the study
- General UGT inhibitors including probenecid, valproic acid within 7 days prior to the study treatment and during the study
- Use of other investigational drugs at the time of enrollment, or within 30 days or 5 half-lives of starting the study treatment or longer if required by local regulations. Any other limitation of participation in an investigational trial based on local regulations
- Use of any medications that are contraindicated in patients with renal impairment
- Use of any drugs with known toxicity to a major organ system within the past 3 months (i.e., cytostatic drugs)
- Unless allowed by the study protocol, use of any other prescription drugs, new herbal supplements, within four (4) weeks prior to initial dosing, and/or over-the-counter (OTC) medication, new dietary supplements (vitamins included), within 3 days prior to initial dosing. If needed, acetaminophen or ibuprofen is acceptable for incidental and limited use.

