11.1 Analysis sets

For all analysis sets, subjects will be analyzed according to the study treatment(s) received.

The safety analysis set will include all subjects that received any study drug.

The PK analysis set will include all subjects with at least one available valid (i.e. not flagged for exclusion) PK concentration measurement, who received any study drug and with no protocol deviations that impact on PK data.

The PD analysis set will include all subjects with available PD data and no protocol deviations with relevant impact on PD data.

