The template shows the analysis / results to be presented in the FIR. Study outputs required to be created at the time of the FIR will be highlighted in TFL shells document and marked as “Key” in the Programming Deliverables Tracker (PDT) output list.

FIR will focus on the following analyses:

- Analysis of populations (if needed)
- Subject disposition
- Demographics and baseline characteristics. Baseline characteristics include, but not limited to:
 - Age, Weight/Height/BMI, Diabetes status, UGE24
- Safety results include, but are not limited to:
 - Number and percentage of subjects with adverse events by body system and preferred term with a breakdown by renal function
- Pharmacokinetic (PK) results for plasma:
 - Arithmetic mean (SD) plasma PK concentration-time plot per renal function (overlying).
 - Summary statistics for PK parameters.
- Pharmacodynamic (PD) analyses include, but are not limited to:

- Model estimated renal function comparison in UGE24, change from baseline and % change from baseline in UGE24.
- Arithmetic mean (SD) UGE24 plot per renal function (overlying) over time

3 Interim analyses

An interim analysis may be initiated once approximately half of the enrolled subjects have completed the study. The purpose of the analysis will be to assess the impact of reduced renal function on UGE24 in order to inform development decisions for LIK066. Actions such as early termination of the study should objectives be met, adjustments to the sample size, and/or revisions of the dose may be made.

Additional interim analyses may be conducted to support decision making concerning the current clinical study, the sponsor’s clinical development projects in general or in case of any safety concerns. The clinical team may communicate interim results to relevant Novartis teams for information, consulting and/or decision purposes.

4 Statistical methods: Analysis sets

For all analysis sets, subjects will be analyzed according to the study treatment(s) received.

The safety analysis set will include all subjects that received any study drug.

The PK analysis set will include all subjects with at least one available valid (i.e. not flagged for exclusion) PK concentration measurement, who received any study drug and experienced no protocol deviations that impact on PK data.

The PD analysis set will include all subjects with available PD data, who received any study drug and experienced no protocol deviations with relevant impact on PD data.

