The analysis sets and protocol deviation codes are related as follows:

Table 4-1 Protocol deviation codes and analysis sets

Category Deviation code	Text description of deviation	Data exclusion
Subjects are excluded from PD and PK analysis in case of these protocol deviations:		Exclude subject from PD and PK analysis set
COMD01	Subject received prohibited concomitant medication	

If updates to this table are needed, an amendment to the SAP needs to be implemented prior to DBL.

5 Statistical methods for Pharmacokinetic (PK) parameters

All subjects within the PK analysis set will be included in the PK data analysis.

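### SAP Table 4-1 removes every PD and PK value of a subject who took a prohibited drug, even a Day 7 UGE24 completed before the first intake; an exclusion tied to timing would be better and costs little

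*SAP*

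**What the plan says.** SAP Section 4 admits a subject to the PD set if the subject "experienced no protocol deviations with relevant impact on PD data", and to the PK set if the subject "experienced no protocol deviations that impact on PK data". Protocol 11.1 has the same condition for the PD set ("no protocol deviations with relevant impact on PD data") and an equivalent one for the PK set.

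Table 4-1 then turns these definitions into codes. Its lead-in reads "The analysis sets and protocol deviation codes are related as follows". The only code listed is COMD01, receipt of a prohibited concomitant medication, and the action is "Exclude subject from PD and PK analysis set". Nothing limits this by drug, date or effect on the data. The SAP allows the table to be changed by amendment before database lock.

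On timing, protocol 3.1 states: "Subjects will remain domiciled up to Day 8 to complete 24-hour collection of urine and blood for urinary glucose excretion". PK sampling goes on after that: "samples for pharmacokinetic assessments will be taken on Days 9, 10 and 11". Several bans in exclusion criterion 20 cover the whole study, for example "Use of SGLT2 or alpha-glucosidase inhibitors within 2 weeks prior to dosing and during the study".

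Protocol 5.2 says that subjects given a prohibited drug *may* need to stop treatment. Protocol 7.2 lists such use among the circumstances in which treatment *must* stop.

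**The concern.** The set definitions ask whether a deviation affected the data. The table that applies them asks only whether it happened. Values that the intake cannot have affected may therefore be lost.

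Take a subject with diabetes who stopped an SGLT2 inhibitor for the study and resumes it on Day 9. The Day 7 UGE24, the primary PD endpoint, was complete on Day 8. Under the SAP Section 4 definition the subject stays in the PD set; under Table 4-1 the subject leaves it.

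Groups are small (10 planned, at least 8 completers assumed in protocol 11.7), and SAP 6.1.3 extracts contrasts within diabetic status. With about half of each impaired group expected to have T2DM (protocol 3.1), a cell holds about 4 to 5 subjects. The SAP already allows for a comparator cell with no data. One valid value counts for most there.

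**Working it through.** **1. Where the texts differ**

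| First intake of the prohibited drug | SAP Section 4 / protocol 11.1 | Table 4-1 |
|---|---|---|
| Within a pre-dose washout window, with impact | Subject out | Subject out |
| Between Day 1 and the Day 7 collection, affecting later data | Subject out, because the sets are defined by subject | Subject out |
| After the Day 7 collection, before Day 11 | Stays in the PD set; PK set depends on impact on the Day 9 to 11 samples | Out of both sets |

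The third row is the clear conflict. In the second row the two texts agree. Keeping Day 1 values there would fit SAP 6.1.3.1, which analyses UGE24 on all available data under missing at random: a subject who stops on Day 3 for an adverse event keeps Day 1 values, while one who stops on Day 3 for a prohibited drug loses them.

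**2. Timing shares**

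Hours from first dose: Day 7 dose 144; Day 7 UGE24 complete 168; last visit 144 + 96 = 240.

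Assume that the drug starts after the first dose and that every hour is equally likely:
- start after the Day 7 collection: (240 − 168)/240 = 30%;
- start after Day 1 is complete: (240 − 24)/240 = 90%.

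These are not shares of all COMD01 cases, because many bans in criterion 20 begin before dosing. If half the cases were pre-dose (assumption), the shares would be 15% and 45%.

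The documents give no frequency. With 0 to 2 cases among 50 subjects (assumption), all after first dose, the recoverable numbers are 0 to 2 × 0.30 = 0.6 Day 7 UGE24 values and 0 to 2 × 0.90 = 1.8 Day 1 profiles. With half the cases pre-dose they are 0 to 0.3 and 0 to 0.9.

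**3. The plan's own precision figure**

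Inputs from protocol 11.7: SD 24 g, 8 completers per group, two-sided 90% CI. Half-width = t(0.95, df) × 24 × √(1/n₁ + 1/n₂). With df = 7: 1.895 × 24 × 0.5 = 22.7 g, the stated value. With the usual two-group df of 14: 1.761 × 24 × 0.5 = 21.1 g.

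**4. Value of one recovered Day 7 UGE24**

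Cells of 4 are 8 completers split about evenly by diabetic status. The pooled df is an approximation to the single MMRM of SAP 6.1.3: 40 subjects (five groups of 8) less about 13 mean parameters per day (10 cells plus 3 covariates) gives about 27.

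| Contrast | df | Without the value | With the value | Gain |
|---|---|---|---|---|
| Stratum, 3 v 4 to 4 v 4 | two-cell, 5 then 6 | 2.015 × 24 × 0.764 = 36.9 g | 1.943 × 24 × 0.707 = 33.0 g | 4.0 g |
| Stratum, 3 v 4 to 4 v 4 | about 27 | 1.703 × 24 × 0.764 = 31.2 g | 1.703 × 24 × 0.707 = 28.9 g | 2.3 g |
| Group, 7 v 8 to 8 v 8 | two-group, 13 then 14 | 1.771 × 24 × 0.5175 = 22.0 g | 1.761 × 24 × 0.5 = 21.1 g | 0.9 g |
| Group, 7 v 8 to 8 v 8 | about 27 | 1.703 × 24 × 0.5175 = 21.2 g | 1.703 × 24 × 0.5 = 20.4 g | 0.7 g |

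Gains are taken before rounding.

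**5. Value of one recovered Day 1 profile**

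The Cmax CV of 22% (protocol 11.7) gives a log SD of √ln(1 + 0.22²) = 0.2174. The CI multipliers exp(± t × 0.2174 × √(1/n₁ + 1/n₂)), with two-cell df, go from 0.72–1.40 to 0.74–1.35 within a stratum and from 0.82–1.22 to 0.83–1.21 at group level.

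**The case against.** The strongest reply is that Table 4-1 is the sponsor's advance judgement that any prohibited drug affects the data. A fixed rule is defensible in an open-label study, since it leaves no room for case-by-case decisions. The Data Management Plan, which is not available here, may also say how COMD01 is assigned. This stands in part: a fixed rule is desirable. But no text presents the table as such a judgement, the list includes drugs with no stated link to LIK066 PK or UGE24 (potassium binders), and no judgement of impact can hold for an intake after the collection has ended. A timing rule is just as fixed.

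A reader might infer that losing Day 1 PK after a Day 3 start also breaks the plan's own definition. It does not. The sets are defined by subject, and a drug that affects Day 7 removes the whole subject under SAP Section 4 too.

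A reader might also infer that the difference between protocol 5.2 and 7.2 changes who is analysed. It does not: COMD01 applies whether or not dosing stops, and a site that follows 7.2 also satisfies 5.2.

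Two limits on size also stand. The 30% and 90% shares leave out pre-dose violations, and the two-cell intervals overstate the gain compared with a pooled model. Replacement subjects, for which protocol 6.3 provides numbering, could restore the counts.

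**Conclusion.** The point holds in a narrow form. Table 4-1 conflicts with SAP Section 4 and protocol 11.1 when the intake cannot have affected the data, most clearly for a start between the end of the Day 7 collection on Day 8 and Day 11. The loss is then a complete primary PD value. For starts between Day 1 and Day 7 that affect later data, keeping the completed Day 1 values is a cheap improvement, not the correction of a contradiction.

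The change is optional. A reader might conclude that the primary analysis is unsound; the documents do not support that. The expected recovery is below one Day 7 value across the trial under the assumptions above (0 to 2 cases, uniform start after first dose), and one such value narrows the half-width by 2.3 to 4.0 g within a stratum or 0.7 to 0.9 g at group level. These sizes rest on SD 24 g, 8 completers per group, an even split by diabetic status and the approximate pooled df.

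**What to change.** 1. Add a note to COMD01 in Table 4-1: *Exclude only UGE24 and PK values not completed before first intake of the prohibited drug; values completed earlier are kept. If intake follows the Day 7 24-hour collection, later concentrations and urine are flagged, and Day 7 parameters that need them (AUClast, AUCinf, T1/2, Vz/F, and CLr if based on urine after 24 h) are set to missing. Use within a pre-dose washout window removes all values.*
2. Reword the set definitions in SAP Section 4 so that a subject with some unaffected PK or PD values stays in the set for those values. Without this, the note would contradict the subject-level definitions. Protocol 11.1 carries the same definitions and should follow at its next amendment.
3. Optionally, change *may need to* in protocol 5.2 to *must*, with a reference to 7.2, at the next protocol amendment.

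Items 1 and 2 need one SAP amendment before database lock, the route that the SAP itself sets for the table. The PK set already recognises concentrations flagged for exclusion, so the note extends an existing practice. The cost is slightly more programming and subjects with partial data in the sets. No visits or samples are added.

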5.1 Variables

The following pharmacokinetic parameters will be determined using the actual recorded sampling times and non-compartmental method(s) with Phoenix WinNonlin (Version 6.2 or higher) from the plasma concentration-time data:

- Primary PK endpoints: C_{max}, T_{max}, AUC_{tau}, AUC_{last}, T_{1/2}, CL/F
- Secondary PK endpoints: V_z/F and CL_r

Additional PK parameters (R_{acc}, T_{1/2acc}, C_{min,ss}, C_{av,ss}, T_{last}, C_{last} etc.) may be calculated or reported as appropriate.

The total amount of LIK066 excreted into urine (A_{e0-t}) will be used to calculate the renal clearance (CL_r) of LIK066 based on both plasma and urine data if the data allows. Plasma sample will be collected for protein binding analysis in order to determine the unbound fraction of LIK066. Accordingly, unbound PK parameters [AUC_u and C_{max,u}] may be calculated.

5.2 Descriptive analyses

LIK066 plasma concentration data will be listed by renal function, diabetic status, subject, and visit/sampling time point. Descriptive statistics will be provided by renal function and visit/sampling time point, including the frequency (n, %) of concentrations below the LLOQ and reported as zero.

Summary statistics will include mean (arithmetic and geometric), SD, CV (arithmetic and geometric), median, minimum, and maximum. Concentrations below LLOQ will be treated as zero in the summary statistics. A geometric mean will not be reported if the dataset includes zero values.

Each of the PK parameters will be listed by renal function, subject, and day and summarized by renal function and day. Descriptive statistics will include mean (arithmetic and geometric), SD, CV (arithmetic and geometric), median, minimum, and maximum. An exception to this is T_{max} where median, minimum, and maximum will be presented.

5.3 Statistical model, assumptions and hypotheses

The natural logarithm of each PK parameter will be analyzed using a MMRM model with diabetic status, renal function group, day, and all associated interactions (where possible) as fixed factors and age as covariate. An unstructured covariance matrix will be used.

For each parameter, the least-square geometric mean will be estimated for each diabetic status by renal function by day combination. In addition, the geometric mean ratio of each renal impaired group to the group with normal renal function and the corresponding two-sided 90%

confidence interval and p-value for the ratio will be extracted for each diabetic status by day combination.

Statistical analysis may be performed to compare the free fraction (f_u) across the renal function groups. If statistically significant difference exists in f_u across renal function groups, the same analysis (as planned for total parameters) will also be performed to compare the $AUC_{0-\infty,u}$ and $C_{max,u}$ between renal function groups. [REDACTED]

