1.3.1 Primary objectives

- To assess the effect of a 7-day treatment with LIK066 on 24-hour urinary glucose excretion (UGE) in subjects with decreased renal function compared to those with normal renal function
 - 24-hour urinary glucose excretion on Day 7
- To assess the pharmacokinetics of LIK066 on Day 1 and Day 7 in subjects with decreased renal function compared to those with normal renal function.
 - C_{max}, T_{max}, AUC_{tau}, AUC_{last}, AUC_{inf}, T_{1/2}, CL/F, V_z/F, CL_r

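### Day 7 unbound exposure is compared only on AUC0-inf,u and Cmax,u and only after a significant free-fraction test; for total drug, AUCtau should be named the lead Day 7 contrast

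*SAP*

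**What the plan says.** **Total drug.** SAP 5.1 gives "Primary PK endpoints: C_{max}, T_{max}, AUC_{tau}, AUC_{last}, T_{1/2}, CL/F". SAP 5.3 then says "The natural logarithm of each PK parameter will be analyzed using a MMRM model", and for each impaired group against normal the "confidence interval and p-value for the ratio will be extracted for each diabetic status by day combination". Days are therefore kept apart. The protocol's list of PK definitions ends AUCtau at the dosing interval, which is 24 h here, and AUClast at the last quantifiable concentration. Protocol 3.1 continues PK sampling to Day 11, 96 h after the final dose.

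**Unbound drug.** SAP 5.1 says "Accordingly, unbound PK parameters [AUC_u and C_{max,u}] may be calculated". SAP 5.3 sets the condition for comparing groups: "If statistically significant difference exists in f_u across renal function groups, the same analysis (as planned for total parameters) will also be performed", and names AUC0-inf,u and Cmax,u as the quantities. The SAP text right after that sentence is redacted. Protocol 11.4.2 carries the same condition in unredacted text, but speaks of AUCu without fixing its window.

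**AUCinf.** SAP 1.3.1 lists "C_{max}, T_{max}, AUC_{tau}, AUC_{last}, AUC_{inf}, T_{1/2}, CL/F, V_z/F, CL_r". Protocol 2.1 and 11.4.1 also include AUCinf, and Protocol 11.4.2 models it where applicable. SAP 5.1 omits it.

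**The concern.** The second primary objective is the effect of renal function on LIK066 exposure. After the seventh daily dose, the area beyond 24 h contains drug left from the earlier doses as well as from the last one. At steady state AUCtau depends on dose and clearance only. An area running to 96 h or to infinity also depends on half-life, and AUClast depends in addition on where each profile falls below the LLOQ. Altered elimination is what a renal PK study looks for, so half-lives may well differ between groups.

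For total drug, the report could then show two primary Day 7 area ratios that differ, with no lead named beforehand.

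For unbound drug there are two consequences. The comparison may not be run at all, because it waits on a significance test in groups of about 8 to 10. If it is run, the Day 7 area used is one that can misstate the steady-state ratio.

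**Working it through.** **Inputs from the documents:** once-daily dosing for 7 days, so tau = 24 h (Protocol 6.2); half-life 10 to 16 h (Protocol 1); Day 7 sampling to 96 h (Protocol 3.1); Cmax CV 22%, at least 8 completers per group, two-sided 90% CI (Protocol 11.7).

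**Assumed, because the documents do not give them:** one-compartment kinetics, ka 1/h, the clearance ratios, the position of concentrations relative to the LLOQ, and the free-fraction CV.

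**1. The plan's own PK precision.** s = sqrt(ln(1 + 0.22²)) = 0.217. With t(0.95, 7 df) = 1.895, the half-width on the log scale is 1.895 × 0.217 × sqrt(2/8) = 0.206, so the factors are exp(±0.206) = 0.81 and 1.23, as stated. (With 14 pooled df they would be 0.83 and 1.21.) The factor 1.23 serves below as a yardstick only.

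**2. Steady-state formula without an absorption phase.** With k = ln 2 / half-life, AUC(0–T)/AUCtau = (1 − e^(−kT)) / (1 − e^(−24k)).
- 10 h: to 96 h, 0.9987/0.8105 = 1.232; to infinity, 1/0.8105 = 1.234.
- 16 h: to 96 h, 0.9844/0.6464 = 1.523; to infinity, 1/0.6464 = 1.547.

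If clearance is equal, the AUCtau ratio is 1.00. A 16 h group against a 10 h group then gives 1.523/1.232 = 1.24 to 96 h and 1.547/1.234 = 1.25 to infinity. The first is about the size of the 1.23 yardstick. Smaller half-life differences give less: to 96 h, 10 against 11 h gives 1.04, 10 against 12 h gives 1.08, and 10 against 13 h gives 1.12.

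**3. Seven oral doses, ka 1/h: impaired/normal ratio after the Day 7 dose.** The first three rows change clearance only and span normal half-lives of 10, 12 and 16 h. The last two keep clearance equal and change half-life through volume.

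| Case | AUCtau | 0–48 h | 0–72 h | 0–96 h | AUCinf |
|---|---|---|---|---|---|
| True ratio 1.2 | 1.198–1.200 | 1.256–1.262 | 1.286–1.293 | 1.295–1.314 | 1.298–1.336 |
| True ratio 1.6 | 1.584–1.599 | 1.777–1.819 | 1.918–1.941 | 1.979–2.011 | 2.008–2.140 |
| True ratio 0.8 | 0.80 | 0.753–0.756 | 0.729–0.743 | 0.719–0.740 | 0.711–0.739 |
| Equal clearance, 12 to 16 h | 0.999 | 1.082 | 1.126 | 1.146 | 1.160 |
| Equal clearance, 10 to 16 h | 0.999 | 1.137 | 1.207 | 1.237 | 1.255 |

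**4. Last quantifiable time (steady-state formula, assumed samples at 24, 48, 72 and 96 h).**
- Both groups end at 24 h: AUClast equals AUCtau, and the two ratios agree whatever the half-lives.
- Equal half-lives of 12 h, true ratio 2, normal 24 h concentration 3 times the LLOQ: the normal group falls to 0.75 times the LLOQ at 48 h and ends at 24 h; the impaired group is at 1.5 times and ends at 48 h. The AUClast ratio is 2 × (1 − 1/16)/(1 − 1/4) = 2.5.

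The gap therefore turns on half-life and last quantifiable time together.

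**5. Unbound drug.** With unbound area = fu × total area, the unbound ratio is the fu ratio times the total ratio, and the factors in steps 2 and 3 pass straight into AUC0-inf,u on Day 7. For the gate, assume an F test on log fu, 5 groups of 8, one group 30% higher, alpha 0.05. The noncentrality is 8 × (ln 1.3)² × 4/5 / ln(1 + CV²), with 4 and 35 df:

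| Assumed fu CV | 15% | 20% | 25% | 30% | 40% |
|---|---|---|---|---|---|
| Noncentrality | 19.8 | 11.2 | 7.3 | 5.1 | 3.0 |
| Power | 93% | 71% | 50% | 36% | 21% |

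Unless fu varies little, the gate would often stay shut on a 30% difference.

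**The case against.** For total drug the opposing case is strong and largely stands. Day 7 AUCtau and CL/F are already planned, and T1/2, which would explain a divergence, is a primary endpoint beside them. The protocol's definitions already tell a PK reader which area belongs to the dosing interval. The analysis is estimation with 90% CIs; no no-effect boundary or success rule depends on a ranking.

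Several stronger readings are tempting, and the documents do not support them:
- *That the two Day 7 ratios disagree whenever half-life differs, or agree whenever it does not.* Step 4 shows exceptions both ways.
- *That SAP 5.1 and 5.3 contradict each other on unbound drug.* One covers deriving the values, the other comparing groups; Protocol 8.7 and 11.4.2 have the same two stages.
- *That SAP 5.2 forbids modelling Tmax.* It governs descriptive statistics. The difference between SAP 5.3 and the shorter modelled list in Protocol 11.4.2 is tidying.

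It can also be said that the gate is a legitimate way to limit output, that the redacted SAP text may qualify it, and that the power figures rest on assumed CVs. The last two are true and limit confidence. But the same gate is unredacted in Protocol 11.4.2, and a non-significant test with about 8 to 10 per group is weak evidence that free fraction is equal.

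**Conclusion.** The point holds as a minor one. For total drug it is a clarification: the correct Day 7 estimate is planned but not named as the lead. For unbound drug it is a change to a stated rule: as written, the SAP can skip the comparison or, on Day 7, run it on an area that includes carry-over and that its own parameter list omits.

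In the illustrations, a true ratio of 1.6 becomes 1.98 to 2.01 for an area to 96 h and 2.01 to 2.14 for AUCinf, and an unchanged steady-state exposure can appear as 1.24 to 1.25. These rest on one-compartment kinetics and assumed clearance ratios. The documents give neither the renal share of clearance, nor half-life by renal group, nor concentrations relative to the LLOQ, nor a free-fraction CV. The actual size is therefore unknown; for AUClast it is nil if the last quantifiable sample is at 24 h in both groups.

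A reader might infer that the plan has no valid estimate of steady-state exposure, or that error control is breached. Neither follows: Day 7 AUCtau is there for total drug, and no formal PK decision rule exists.

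**What to change.** In SAP 5.1 and 5.3:

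1. Report Day 7 AUCtau,u and Cmax,u ratios with 90% CIs whenever free-fraction data exist, and remove the significance condition.
2. Name Day 7 AUCtau, with Cmax, as the lead Day 7 exposure contrast. Label Day 7 AUClast, and Day 7 AUCinf if derived, as supportive.
3. Leave the Day 1 parameters and the T1/2 and CL/F comparisons unchanged.
4. Align the AUCinf listing across SAP 1.3.1, 5.1 and 5.3 and Protocol 2.1 and 11.4.1.

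The cost is SAP wording and a little more output. No new samples are needed: AUCtau is already derived and plasma for protein binding is already collected. If the sponsor also chooses to change Protocol 11.4, that requires a written amendment with the approvals in Protocol 13.1.
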